COVER PAGE FOR PROTOCOL AND STATISTICAL ANALYSIS PLAN

Official Study Title: SGLT2 Inhibition and Stimulation of Endogenous Glucose Production:
Protocol 2

NCT number: NCT02592421

IRB Approval Date: 09/06/2017

Protocol Template Form

Item 1 UTHSCSA Tracking Number	HSC20150668H
-----------------------------------	--------------

Item 2 Abstract / Project Summary	
Provide a succinct and accurate description of the proposed research. State the purpose/aims. Describe concisely the research design and methods for achieving the stated goals. This section should be understandable to all members of the IRB, scientific and non-scientific.
 
DO NOT EXCEED THE SPACE PROVIDED.

------------------------------------------	---------------------------------------------------------------------------------------------------------------------------------------------------------------------------------------------------------------------------------------------------------------------------------------------------------------------------------------------------------------------

Purpose/Objectives: We will determine the role of pancreatic hormones (increase in plasma glucagon and decrease in plasma insulin concentration) in the stimulation of EGP following SGLT2 inhibition.

Research Design/Plan: After screening, eligible subjects will receive three 5-hour measurements of EGP with administration of study drug after a 3-hour tracer equilibration period. HGP will be measured for 5 hours after drug administration to allow sufficient time for a significant increase in HGP above baseline after dapagliflozin administration (10). In study 1, HGP will be measured for 5 hours after dapagliflozin (10 mg) or placebo administration. Study 2 will be performed under glucose clamp conditions (i.e. maintaining the plasma glucose concentration stable at each subject's fasting level), and Study 3 will be performed under pancreatic clamp conditions (maintaining the plasma glucagon and insulin concentrations constant at the basal level). Subjects will be randomized in a 2:1 ratio; 20 subjects will receive dapagliflozin and 10 subjects will receive placebo. Each study will be performed on a separate day, after a 10-12 hour overnight fast within 1-2 week period.

Methods: Screening visit; Study 1 EGP, Study 2 EGP with Glucose Clamp, Study 3 EGP Pancreatic Clamp

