Type 2 Diabetic subjects	18-70 yrs old BMI = 25-45 kg/m ² HbA1C < 10% Other than diabetes, subjects must be in good general health as determined by physical exam, medical history, blood chemistries, CBC, TSH, T4, EKG and urinalysis Only subjects whose body weight has been stable (\pm 3 lbs) over the preceding three months and who do not participate in an excessively heavy exercise program will be included.	Subjects taking drug known to affect glucose metabolism (other than metformin and sulfonylurea) Individuals with evidence of proliferative diabetic retinopathy, plasma creatinine >1.4 females or >1.5 males, or 24-hour urine albumin excretion > 300 mg will be excluded.

Item 6

Research Plan / Description of the Research Methods a. *Provide a comprehensive narrative describing the research methods. Provide the plan for data analysis (include as applicable the sample size calculation).*

Step-by-Step Methods: Screening Visit. Medical history is obtained and physical exam performed. Blood is drawn for FPG, blood chemistries, lipid profile, HbA1c, and thyroid function. Urine analysis, EKG and pregnancy test are performed.

Study 1: Effect of Dapagliflozin on EGP: EGP will be measured with 3-³H-glucose infusion. The 3-³H-glucose infusion will be started at 6 AM and arterialized blood samples will be drawn from a catheter placed retrogradely in a vein on the dorsum of the hand to measure the basal rate of EGP. The hand will be placed in a box heated to 70°C to ensure arterialization of the venous blood. After a 3 hour tracer equilibration period (at 9 AM) subjects will receive dapagliflozin (10 mg) or placebo, and blood samples will be drawn every 10-20 minutes for 5 hours (until 2 PM) for the measurement of plasma glucose, insulin, C-peptide, glucagon, cortisol, catecholamine concentrations and [3-³H]-glucose specific activity. Urine will be collected from 6 to 9 AM and from 9 AM to 2 PM. Urinary volume and glucose conc will be measured and the rate of urinary glucose excretion quantitated. The study will end at 2 PM and subjects will be allowed to return home. Basic metabolic panel will be performed during the study to monitor renal function.

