Study 3: Effect of Dapagliflozin on EGP with Pancreatic Clamp: In this study, EGP will be measured as described in Study 1 above and plasma insulin and glucagon concentrations will be clamped at the basal level using the pancreatic clamp technique, while the plasma glucose concentration will be allowed to decrease spontaneously after dapagliflozin and placebo administration. Somatostatin (750 µg/h) infusion will be started at 5:45 AM (15 minutes before the start of [3-³H]-glucose infusion [6 AM]) along with basal infusions of glucagon (0.3 ng/kg.min) and insulin (0.1 mU/kg.min) to replace basal plasma glucagon and insulin concentrations. The somatostatin, glucagon and insulin infusions will be continued for the entire duration of the study (until 2 PM). At 6 AM a prime (0.4 uCi x FPG) – continuous (0.4 uCi/min) infusion of [3-³H]-glucose will be started and continued to 2 PM. At 9AM, subjects will ingest dapagliflozin (10 mg) or placebo (2:1 randomization ratio) and blood samples will be drawn at -30, -20, -10, 5 and 0 minutes before and every 10-20 minutes after drug administration (until 2 PM) for the measurement of plasma glucose, insulin, C-peptide, glucagon, cortisol, catecholamine concentrations, and plasma [3-³H]-glucose specific activity. Urine will be collected from 6 to 9 AM and from 9 AM to 2 PM. Urinary volume and glucose concentration will be measured and the rate of urinary glucose excretion will be calculated. The study will end at 2 PM. Basic metabolic panel will be performed during the study to monitor renal function.

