EGP measurement with 3- ³ H-glucose	
 ○ Blood draws and cath placement: 
 ○ fainting, pain, bruising, swelling, bleeding, anemia or rarely infection where the needle is inserted. ○ In rare cases the area where the needle is inserted can also become infected or nerves may be damaged, inducing long-lasting abnormal sensations (paresthesia), impaired sensation of touch and persistent pain ○ Some people may experience mild pain from the catheter. On rare occasions, inflammation of the vein may occur or bruising or black and blueness may occur over the puncture site. Such complications occur in less than 1% of individuals and, if they occur, they usually go away on their own in 2-3 days and are helped by using hot packs. ○ Radiation exposure 
There is no known minimum level of radiation exposure that is recognized as being totally free of the risk of causing genetic defects (abnormal cells) or cancer. However, the probability of harm from such risk associated with the amount of radiation exposure received from this study is considered to be low when compared to other everyday risks each member of the general public receives per year, depending on the
 ○ Heated box: 
During visits 2, 3, and 4 , the hand is placed in a transparent plastic thermo regulated box heated to 70°C (158°F). Rarely, the hand may suffer a burn or blister. Please tell us if your hand is too hot or feels uncomfortable while in the heated box, in which case your hand will be removed from the box but the test will be continued.
 ○ Dapagliflozin: 
 ○ Likely and not serious: ○ These risks are expected to occur in more than 20 out of 100 subjects: Nausea ○ ○ Less likely and not serious: ○ These risks are expected to occur in 5-20 subjects or less out of 100 subjects: vomiting, diarrhea, constipation, GI upset, dizziness, fatigue, headache, runny nose, and in less than 4 out of 100 individuals low blood sugar (also called Hypoglycemia), urinary tract (about 1%) and genital infections (about 4%) ○ ○ Rare and serious: loss of consciousness (or syncopy), decrease in blood pressure (less than 1%), and bladder cancer (less than 0.2%). ○ ○ Safety considerations for dapagliflozin and other SGLT2 inhibitors: ○ Dapagliflozin – is a sodium-glucose cotransporter 2 (SGLT2) inhibitor indicated as an adjunct to diet and exercise to improve glycemic control in adults with type 2 diabetes mellitus and is a member of a class of antidiabetic medications that work by increasing the glucose excretion in the urine. Dapagliflozin (FARXIGA) has been approved by the U.S. FDA. Side effects reported with dapagliflozin will be summarized below based upon http://www1astrazeneca-us.com/pi/pi_faxiga.pdf ○ ○ Hypotension ○ Dapagliflozin may cause intravascular volume contraction. Symptomatic hypotension can occur after initiating dapagliflozin particularly in patients with impaired renal function (eGFR less than 60 ±5 mL/min/1.73 m²), elderly patients, or patients on loop diuretics. Subjects with eGFR less than 60 ±5 mL/min/1.73 m² will not be allowed in the study. Signs and symptoms of hypotension after initiating therapy will be monitored. If a participant experiences any of these, the dapagliflozin will be stopped and the participant will be discontinued from the study. ○ Renal Function ○ A small decrease in kidney function (eGFR) and increase in serum creatinine has been observed when dapagliflozin is initially started. The eGFR gradually returns toward normal while the drug is continued and returns to normal if drug is stopped. If the eGFR drops below 60 or if the serum creatinine rises by ≥3.0 mg/dl the dapagliflozin will be stopped and the participant will be discontinued from the study. Sudden kidney injury (acute kidney injury) has happened to people taking dapagliflozin. Talk to your doctor right away if you: 
 ○ reduce the amount of food or liquid you drink for example, if you are sick or cannot eat or ○ you start to lose liquids from your body for example, from vomiting, diarrhea or being in the sun too long. Seek medical attention immediately if you experience signs and symptoms while taking these medicines such as: 
 ○ Decreased urine ○ Swelling in your legs or feet ○ Hypoglycemia ○ Hypoglycemia (low blood sugar) – can occur with any antidiabetic medication. In studies of dapagliflozin, the frequency of hypoglycemia was less than 5% and similar to that in the placebo group. Subjects will be told to call the investigator if symptoms (sweating, rapid thumping heartbeat, mental confusion) of hypoglycemia occur and to drink a glass of orange juice with a packet of sugar. Any subjects with hypoglycemia will be evaluated for potential causes. If the hypoglycemia recurs, the subject will be discontinued from the study.

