EGP measurement with 3-3H-glucose with Glucose Clamp	
 ○ Blood draws and cath placement: 
 ○ fainting, pain, bruising, swelling, bleeding, anemia or rarely infection where the needle is inserted. ○ In rare cases the area where the needle is inserted can also become infected or nerves may be damaged, inducing long-lasting abnormal sensations (paresthesia), impaired sensation of touch and persistent pain ○ Some people may experience mild pain from the catheter. On rare occasions, inflammation of the vein may occur or bruising or black and blueness may occur over the puncture site. Such complications occur in less than 1% of individuals and, if they occur, they usually go away on their own in 2-3 days and are helped by using hot packs. ○ Radiation exposure 
There is no known minimum level of radiation exposure that is recognized as being totally free of the risk of causing genetic defects (abnormal cells) or cancer. However, the probability of harm from such risk associated with the amount of radiation exposure received from this study is considered to be low when compared to other everyday risks each member of the general public receives per year, depending on the
 ○ Heated box: 
During visits 2, 3, and 4 , the hand is placed in a transparent plastic thermo regulated box heated to 70°C (158°F). Rarely, the hand may suffer a burn or blister. Please tell us if your hand is too hot or feels uncomfortable while in the heated box, in which case your hand will be removed from the box but the test will be continued.
 ○ Dapagliflozin: 
 ○ Likely and not serious: ○ These risks are expected to occur in more than 20 out of 100 subjects: Nausea ○ ○ Less likely and not serious: ○ These risks are expected to occur in 5-20 subjects or less out of 100 subjects: vomiting, diarrhea, constipation, GI upset, dizziness, fatigue, headache, runny nose, and in less than 4 out of 100 individuals low blood sugar (also called Hypoglycemia), urinary tract (about 1%) and genital infections (about 4%) ○ ○ Rare and serious: loss of consciousness (or syncopy), decrease in blood pressure (less than 1%), and bladder cancer (less than 0.2%). ○ ○ Safety considerations for dapagliflozin and other SGLT2 inhibitors: ○ Dapagliflozin – is a sodium-glucose cotransporter 2 (SGLT2) inhibitor indicated as an adjunct to diet and exercise to improve glycemic control in adults with type 2 diabetes mellitus and is a member of a class of antidiabetic medications that work by increasing the glucose excretion in the urine. Dapagliflozin (FARXIGA) has been approved by the U.S. FDA. Side effects reported with dapagliflozin will be summarized below based upon http://www1astrazeneca-us.com/pi/pi_faxiga.pdf ○ ○ Hypotension ○ Dapagliflozin may cause intravascular volume contraction. Symptomatic hypotension can occur after initiating dapagliflozin particularly in patients with impaired renal function (eGFR less than 60 ±5 mL/min/1.73 m²), elderly patients, or patients on loop diuretics. Subjects with eGFR less than 60 ±5 mL/min/1.73 m² will not be allowed in the study. Signs and symptoms of hypotension after initiating therapy will be monitored. If a participant experiences any of these, the dapagliflozin will be stopped and the participant will be discontinued from the study. ○ Renal Function ○ A small decrease in kidney function (eGFR) and increase in serum creatinine has been observed when dapagliflozin is initially started. The eGFR gradually returns toward normal while the drug is continued and returns to normal if drug is stopped. If the eGFR drops below 60 or if the serum creatinine rises by ≥3.0 mg/dl the dapagliflozin will be stopped and the participant will be discontinued from the study. Sudden kidney injury (acute kidney injury) has happened to people taking dapagliflozin. Talk to your doctor right away if you: 
 ○ reduce the amount of food or liquid you drink for example, if you are sick or cannot eat or ○ you start to lose liquids from your body for example, from vomiting, diarrhea or being in the sun too long. Seek medical attention immediately if you experience signs and symptoms while taking these medicines such as: 
 ○ Decreased urine ○ Swelling in your legs or feet ○ Hypoglycemia ○ Hypoglycemia (low blood sugar) – can occur with any antidiabetic medication. In studies of dapagliflozin, the frequency of hypoglycemia was less than 5% and similar to that in the placebo group. Subjects will be told to call the investigator if symptoms (sweating, rapid thumping heartbeat, mental confusion) of hypoglycemia occur and to drink a glass of orange juice with a packet of sugar. Any subjects with hypoglycemia will be evaluated for potential causes. If the hypoglycemia recurs, the subject will be discontinued from the study.

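### The creatinine limb of the renal stopping rule adds nothing to the eGFR limb, so a 1.5-fold creatinine rise from a low-normal baseline does not stop re-dosing

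*Combined protocol and SAP*

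**What the plan says.** The rule is in Item 7 (Risks Section), under Renal Function, in the row for EGP measurement with 3-3H-glucose: "If the eGFR drops below 60 or if the serum creatinine rises by ≥3.0 mg/dl the dapagliflozin will be stopped", and the participant is then discontinued. The rows for the glucose clamp and the pancreatic clamp repeat it, including "if the serum creatinine rises by ≥3.0 mg/dl". The same paragraph expects a modest, reversible dip in eGFR and goes on to name acute kidney injury as something that has occurred on this drug.

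Dosing is repeated. Item 2 says of the three experiments: "Each study will be performed on a separate day, after a 10-12 hour overnight fast within 1-2 week period". In Item 6, Study 1 reads "After a 3 hour tracer equilibration period (at 9 AM) subjects will receive dapagliflozin (10 mg) or placebo", and Studies 2 and 3 also dose at 9 AM. A baseline creatinine should be available from screening: "Blood is drawn for FPG, blood chemistries, lipid profile, HbA1c, and thyroid function". For each of the three study days Item 6 adds "Basic metabolic panel will be performed during the study to monitor renal function", without a clock time and without saying when the result must be read.

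**The concern.** Two limbs joined by 'or' suggest two safeguards: a floor on eGFR and a check on change from the subject's own baseline. A rise of 3.0 mg/dl is so large that the floor should always be crossed first. If so, the rule contains no working test of change. A subject who starts well above 60 can lose a substantial share of filtration and still be eligible for the next dose.

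At stake is the safety of up to 20 subjects who take dapagliflozin on three days within one to two weeks. The EGP comparison is not at stake.

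**Working it through.** **Inputs from the documents.** Stop at eGFR below 60 or a creatinine rise of at least 3.0 mg/dl (Item 7); ages 18-70 and creatinine ceilings of 1.4 (women) and 1.5 (men), read as mg/dl (Item 5); eGFR expressed per 1.73 m² (Item 7, Hypotension).

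**Assumption.** The eGFR equation. The cover page is dated ("IRB Approval Date: 09/06/2017"), so CKD-EPI 2009 and MDRD are the natural candidates, with CKD-EPI 2021 as a check. S is creatinine, treated as steady-state; κ = 0.9 for men and 0.7 for women.

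- CKD-EPI 2009: 141 × min(S/κ,1)^α × max(S/κ,1)^−1.209 × 0.993^age × 1.018 if female; α = −0.411 (men), −0.329 (women); race coefficient 1.159.
- MDRD: 175 × S^−1.154 × age^−0.203 × 0.742 if female; race coefficient 1.212.
- CKD-EPI 2021: 142 × min(S/κ,1)^α × max(S/κ,1)^−1.200 × 0.9938^age × 1.012 if female; α = −0.302 (men), −0.241 (women).

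The plan derives neither threshold, so it has no figure to reproduce. Results carry no race coefficient unless stated.

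**Step 1: creatinine at which eGFR equals 60.** Example, man aged 45, CKD-EPI 2009: S = 0.9 × (141 × 0.993^45 / 60)^(1/1.209) = 1.41 mg/dl. Over ages 18-70:

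| Equation | Men | Women |
|---|---|---|
| CKD-EPI 2009 | 1.21-1.64 | 0.96-1.30 |
| MDRD | 1.20-1.52 | 0.92-1.17 |
| CKD-EPI 2021 | 1.28-1.68 | 1.01-1.32 |

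The highest value with a race coefficient is 1.86.

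**Step 2: eGFR when the creatinine limb fires.** The most favourable case is a man of 18 with an implausibly low baseline of 0.3, ending at 3.3 mg/dl: 25.8 (CKD-EPI 2009), 24.5 (MDRD), 26.7 (CKD-EPI 2021), and at most 29.9 with a race coefficient. From 0.6 the limb needs 3.6 mg/dl, a 6-fold rise; from the male entry ceiling of 1.5 it needs 4.5, a 3-fold rise. Reading the limb as a level of 3.0 instead of a rise does not help: eGFR is then at most 33.6. In every case the floor of 60 has already been crossed.

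**Step 3: what the floor alone misses.** eGFR after a 1.5-fold rise at ages 45/55/65, with the share lost (1 − eGFR after / eGFR before):

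| Equation | Man 0.8 to 1.2 | Loss | Woman 0.6 to 0.9 | Loss |
|---|---|---|---|---|
| CKD-EPI 2009 | 72.6/67.7/63.1 | 32.7% | 77.2/72.0/67.1 | 29.9% |
| MDRD | 65.5/62.9/60.8 | 37.4% | 67.7/65.0/62.8 | 37.4% |
| CKD-EPI 2021 | 76.0/71.4/67.1 | 31.7% | 80.3/75.5/70.9 | 28.7% |

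The woman is missed at every age from 18 to 70 (lowest value 61.9). The man is missed at every age except 70 under MDRD (59.9). The loss that the floor tolerates is 1 − 60/baseline: 40% from a baseline eGFR of 100 and 48% from 115.

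**Step 4: where the gap ends.** The highest baseline at which a 1.5-fold rise goes unstopped is the Step 1 value divided by 1.5: 0.80-1.12 mg/dl in men and 0.62-0.88 in women, across age and equation. The last ages at which it is missed are:

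| Baseline (man / woman) | CKD-EPI 2009 | MDRD | CKD-EPI 2021 |
|---|---|---|---|
| 0.9 / 0.7 | 51 / 54 | 35 / 33 | 60 / 62 |
| 1.0 / 0.8 | 33 / 31 | 19 / none | 39 / 36 |

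From mid-normal baselines (1.0 and 0.8) the floor therefore catches the rise from age 40. A race coefficient moves these limits to later ages.

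**Step 5: timing.** A panel is planned on each study day and drug is given at 9 AM, but nothing links one day's result to the decision to give the next dose.

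**The case against.** The strongest defence is that a redundant limb in an 'or' rule removes no protection: the eGFR limb still stops the drug long before a 3.0 mg/dl rise. That is true. The gap comes from having no working test of change. The 1.5-fold figure is proposed here and is not in the documents.

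Much else limits the consequence. Exposure is three single doses. Entry requires good general health and caps creatinine and albumin excretion. The drug also stops for hypotension, subjects are told to act on decreased urine, swelling or symptoms of volume depletion, the protocol says eGFR recovers when the drug is stopped, and nothing obliges the investigator to re-dose. All of this stands and keeps the point small. None of these other stops uses creatinine, however.

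Four stronger readings are tempting but not supported:

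- *The creatinine limb can never fire first under any equation.* Unindexed Cockcroft-Gault with actual weight, in a man of 18 with a BMI of 45, gives 72-87 mL/min at a creatinine of 3.5. Item 5 admits that BMI. The protocol's eGFR unit is per 1.73 m², and indexed Cockcroft-Gault gives at most about 48 in the cases tried, so the claim is restricted to indexed equations.
- *The rule misses 1.5-fold rises in general.* Step 4 shows that it does not.
- *3.0 is a misprint.* The figure is the same in three rows, and the documents cannot settle what was intended.
- *The panel must move to before the dose.* If it is the only panel of the day, moving it would give up any post-dose creatinine, including on the last study day, after which no visit is listed.

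**Conclusion.** The point holds, and it is minor. Under any of the three indexed equations assumed, the 3.0 mg/dl limb does no work. The remaining floor lets re-dosing continue after a loss of about 29-37% of eGFR in subjects with low-normal creatinine. The gap is confined to those baselines and narrows with age.

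This describes what the wording permits; it does not predict an event. The documents give no rate of renal events, so the number of subjects affected cannot be estimated. The conclusion rests on an indexed eGFR and on creatinine treated as steady-state; in acute injury the true loss could be larger than calculated. A reader might infer that the trial's results are compromised, but the documents do not support that: the EGP analysis does not depend on this rule.

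**What to change.** In all three rows of Item 7, replace the 3.0 mg/dl limb with a rise to at least 1.5 times the screening creatinine. Keep the eGFR limb as it is. In Item 6, require the previous study day's panel to be reviewed against both limbs before the next dose. The panel need not move to before the dose.

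A factor of 1.5 adds protection where the floor is silent (the baselines in Step 4). A doubling would be redundant at baselines of 0.9 in men and 0.7 in women without a race coefficient: 2 × 0.9 = 1.8 and 2 × 0.7 = 1.4 exceed the highest creatinine values at eGFR 60 of 1.68 and 1.32.

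The cost is the wording of three identical rows, one sentence in Item 6, and an occasional extra withdrawal from a sample of 20 + 10. At baselines of 0.5-0.6 a 1.5-fold rise is only 0.25-0.30 mg/dl, so a repeat sample should confirm it before withdrawal; that is an extra test in those few subjects. The review covers only what has appeared by the time of the previous panel, and injury after the third day's panel remains uncovered.

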Item 3 Background 
Describe past experimental and/or clinical findings leading to the formulation of your study.
 
For research involving unapproved drugs, describe animal and human studies.
 
For research that involves approved drugs or devices, describe the FDA approved uses of this drug/device in relation to your protocol.
	
Insert background: EGP is key to understanding normal glucose homeostasis and development of hyperglycemia in T2DM. We and others have demonstrated that glucosuria produced by SGLT2 inhibition stimulates an increase in EGP, suggesting the presence of a strong interaction between the kidney and liver, i.e. "a reno-hepatic axis" that coordinates the regulation of EGP and plasma glucose concentration. The present study will provide evidence for the presence of this previously unrecognized reno-hepatic axis and define the mechanisms which underlie the interaction between the kidney and liver. In addition to providing novel insights concerning the regulation of glucose homeostasis, the present study has direct and important clinical implications. Although SGLT2 inhibitors are effective in producing glucosuria, they cause only a modest decrease in HbA1c (0.6-0.8%). On one hand, the presence of a "reno-hepatic axis" that leads to a compensatory increase in EGP in response to glucosuria maintains the FPG within the normal range in NGT individuals and prevents hypoglycemia. On the other hand, the increase in EGP in T2DM individuals is "paradoxical" in that it occurs while the plasma glucose concentration is within the hyperglycemic range and quantitatively offsets by ~50% urinary glucose loss (see results below) produced by SGLT2 inhibitors and markedly attenuates their glucose lowering effect. Thus, determining the mechanisms that mediate the rise in EGP in response to glucosuria will allow the development of strategies that prevent the rise in EGP and increase the efficacy of SGLT2 inhibitors. Our preliminary data suggest an important role for increased glucagon secretion in mediating the "reno-haptic" interaction. In the present study, we will examine whether co-administration of the GLP-1 receptor agonist liraglutide with the SGLT2 inhibitor (dapagliflozin) can prevent the compensatory increase in EGP in response to

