Data Analysis Plan: Data Analysis and Statistical Methods: Under steady-state postabsorptive conditions, the basal rate of endogenous glucose appearance ($R_a = bEGP$) equals the 3-³H-glucose infusion rate divided by steady state plasma tritiated glucose specific activity. After drug administration, non-steady conditions for 3-³H-glucose specific activity prevail and the rate of whole body glucose appearance (R_a) is calculated from Steele's equation. During the glucose clamp study, the rate of EGP after drug administration equals R_a minus glucose infusion rate, while, during the pancreatic clamp, $R_a = EGP$ since no cold glucose is infused. The difference in EGP during the last hour of the study (240-300 minute) between subjects receiving dapagliflozin and subjects receiving placebo represents the increase in EGP caused by dapagliflozin (glucosuria-stimulated increase in EGP). The glucosuria-stimulated increase in EGP will be compared among the three studies with ANOVA. Post hoc testing will be performed with a Bonferroni correction for multiple comparisons. The difference in glucosuria-stimulated increase in EGP between study 2 and study 1 represents the contribution

of the decrease in plasma glucose conc to the increase in EGP, while the difference between study 3 and study 1 represents the contribution of change in islet hormones (insulin/glucagon) to the increase in EGP.

Item 7 Risks Section:

Complete the following table to describe the risks of all **research procedures** listed in Step 2, Institutional Form (items 28-34). *Do not list risks of Routine care procedures here.*

N/A, Risks are described in the informed consent document – do not complete this table.

Research procedures	Risks
example: 
• History and physical• Questionnaire• Laboratory tests	List the reasonably expected risks under the following categories as appropriate:
Add or delete rows as needed	

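### The plan foresees drug-related discontinuation between study days but names only ANOVA, with no within-subject model and no rule for participants with incomplete study days

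*Combined protocol and SAP*

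**What the plan says.** **Design (Item 2, Abstract).** "eligible subjects will receive three 5-hour measurements of EGP with administration of study drug after a 3-hour tracer equilibration period". The three studies take place on separate days within one to two weeks, in the same people. No order is stated. "Subjects will be randomized in a 2:1 ratio; 20 subjects will receive dapagliflozin and 10 subjects will receive placebo".

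**Discontinuation (Item 7, Dapagliflozin text, repeated in all three procedure rows).** For signs and symptoms of hypotension: "If a participant experiences any of these, the dapagliflozin will be stopped and the participant will be discontinued from the study". The same consequence follows if eGFR falls below 60 or creatinine rises by 3.0 mg/dl or more. The text attributes both triggers to the drug. It says dapagliflozin may contract intravascular volume, and on renal function: "A small decrease in kidney function (eGFR) and increase in serum creatinine has been observed when dapagliflozin is initially started". A metabolic panel is run in each of the three studies (Item 6), so the eGFR rule can be triggered between study days.

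**Analysis (Item 6, Data Analysis Plan).** The drug effect in each study is the dapagliflozin-minus-placebo difference in EGP at 240-300 minutes. "The glucosuria-stimulated increase in EGP will be compared among the three studies with ANOVA". Study 2 against Study 1 is read as the contribution of the fall in plasma glucose, and Study 3 against Study 1 as the contribution of islet hormones. The plan gives no analysis set, no subject term, no baseline term and no rule for a missed study day.

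**The concern.** A participant discontinued after the first or second study day contributes EGP to the earlier day and nothing to the later one. Two different analyses could then fairly be called ANOVA. One compares the means of whoever was present on each day, so the days are compared in partly different people. The other is a repeated-measures ANOVA on completers, which discards the early days of those who left. If leaving is related to EGP, the two err in opposite directions. With 20 and 10 participants and no rule written down, the choice could be made after the data are seen. What is at stake is the Study 3 against Study 1 contrast, which is the trial's answer on islet hormones, and likewise Study 2 against Study 1.

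**Working it through.** The documents give no power calculation, effect size, SD or dropout rate, so there is no figure of theirs to reproduce beyond the allocation: 20/10 = 2:1, 30 in total.

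**Step 1. How many losses?** Expected losses are 20 × p, and the chance of at least one is 1 − (1 − p)^20. The rates in Item 7 come from other dapagliflozin studies. Applying them to three single doses is an assumption.

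| Route | p | Expected of 20 | At least one |
|---|---|---|---|
| Volume depletion including hypotension | 0.8% | 0.16 | 15% |
| Decrease in blood pressure, upper bound | 1% | 0.20 | 18% |
| eGFR below 60 (no rate given; assumed) | 2% | 0.4 | 33% |
| same, assumed | 5% | 1 | 64% |
| same, assumed | 10% | 2 | 88% |
| same, assumed | 20% | 4 | 99% |

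On placebo the volume-depletion rate is 0.4%, so 10 × 0.004 = 0.04 expected.

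The eGFR rows are only a range. They are worth showing because the entry limit of 60 ±5 can be read as low as 60 − 5 = 55. Someone admitted between 55 and 60 would already meet the stopping limit of 60, and an early fall is expected.

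Dizziness is a second ambiguity. Item 7 lists it among non-serious events ("vomiting, diarrhea, constipation, GI upset, dizziness, fatigue, headache, runny nose") expected in 5-20 or fewer per 100, and does not say whether it counts as a symptom of hypotension. If it did, 5% to 20% would mean 1 to 4 of 20. Because the text says 'or less', 1 is not a lower bound.

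**Step 2. What would losses do to the contrast?** Assumed, not from the documents: between-subject SD 0.35, residual SD 0.20, drug effect 0.50 in Study 1 and 0.25 in Study 3 (mg/kg/min). The true contrast is then 0.25.

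- Total SD = √(0.35² + 0.20²) = √0.1625 = 0.403. Within-subject correlation r = 0.1225/0.1625 = 0.754.
- Suppose k of 20 dapagliflozin participants leave after Study 1, and their Study 1 EGP differs from that of those retained by d SD. Dropping them moves the Study 1 mean by Δ = (k/20) × d × 0.403.
- Available means: only the later-day mean moves, by r × Δ. That is the bias.
- Completers only: both means move, and the bias is (1 − r) × Δ with the opposite sign. The ratio to the available-means bias is 0.246/0.754, about one third.

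| k | Available means, d = 0.5 / 1 | Completers only, d = 0.5 / 1 |
|---|---|---|
| 1 | 3% / 6% | 1% / 2% |
| 2 | 6% / 12% | 2% / 4% |
| 4 | 12% / 24% | 4% / 8% |

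Worked case, k = 4, d = 1: Δ = 0.2 × 0.403 = 0.0806. Available means 0.754 × 0.0806 = 0.061, and 0.061/0.25 = 24%. Completers 0.246 × 0.0806 = 0.020, and 0.020/0.25 = 8%.

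Simulation on the same SDs (20,000 runs per setting, chance of loss depending on Study 1 EGP) agrees: available-means bias is about 3 to 6%, 6 to 12% and 13 to 23% for k = 1, 2 and 4. The sign is negative if low-EGP participants leave and positive if high-EGP participants leave. A likelihood-type estimator using every completed day, with the variance ratio taken as known, was within 1% either way. Purely random loss biases none of the three.

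**Step 3. Against the noise.** The full-data standard error of the within-subject contrast is 0.20 × √2 × √(1/20 + 1/10) = 0.11. The largest bias above, 0.061, is about 0.6 of that; with one loss, 0.015/0.11 is about 0.1.

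**Step 4. The missing subject term.** If ANOVA treated the three studies as independent groups, the standard error would be built on the total SD: 0.403 × √2 × √0.15 = 0.22, twice 0.11. On these assumed SDs that costs more than the likely bias, and it applies even if nobody leaves.

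**The case against.** The strongest reply is that the documents' own rates make losses rare, that the other stopping rules are not arm-selective, and that a repeated-measures ANOVA on the same people may be what is meant. Most of this stands. At 0.8% the likeliest number of losses is zero. Hypoglycemia is put below 5% and similar to placebo, and removes a participant only on recurrence ("If the hypoglycemia recurs, the subject will be discontinued from the study"). Hypersensitivity is 0.3% against 0.2%, and no excess of cardiovascular events is reported. The rules are worded for any participant, so placebo participants can be removed too. What the reply does not answer is the eGFR route, which has no rate and overlapping limits, and the fact that the plan never says which ANOVA is intended.

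A reader might infer more: that weak EGP responders will leave the dapagliflozin arm, so that Studies 2 and 3 are run in a selected group and the hormone contribution is understated. The documents do not support this. The Background sentence that seems to supply the mechanism ("maintains the FPG within the normal range in NGT individuals and prevents hypoglycemia") concerns people with normal glucose tolerance. The trial enrols type 2 diabetics, in whom the Background says the EGP rise occurs at hyperglycemic glucose levels. No passage links hypotension or a falling eGFR to low EGP. The reverse is equally open: glucosuria is said to drive EGP, and the drug's salt and water loss is said to contract volume, so strong responders could be the ones to leave. Study order is not stated either. If Study 3 came first, the same losses would bias the contrast the other way.

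**Conclusion.** The point holds as a gap in the analysis plan, at low severity. Discontinuation for drug effects is foreseen, it removes later study days, and the plan's single word for the comparison fixes neither the within-subject structure nor the treatment of incomplete participants. On documented hypotension and volume-depletion rates about 0.2 of 20 dapagliflozin participants would be lost. The eGFR route could add to that by an unknown amount.

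If losses occur and relate to EGP, available means could be off by roughly 3% to 24% of the assumed contrast for one to four losses, with unknown sign, and completers by about a third of that in the opposite direction. These sizes rest on assumed SDs and effects, on an assumed gap of 0.5 to 1 SD between those lost and those retained, and on loss after Study 1. All lie below one standard error. It does not follow that the groups compared will differ, or that the hormone contribution will be understated.

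**What to change.** In the Data Analysis Plan (Item 6):

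1. Replace ANOVA with a REML mixed model for 240-300 minute EGP with drug, study, drug × study, a subject random effect and same-day pre-dose basal EGP. State that every completed study day is used, including those of participants later discontinued.
2. Estimate Study 2 against 1 and Study 3 against 1 from the drug × study terms, with Bonferroni as already planned.
3. Add a sensitivity analysis limited to participants with both days of the contrast.
4. Tabulate discontinuations by arm, study day and reason.

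The basal term is there for precision, not to handle dropout, and it was not part of the calculation above. In Study 3 it is measured with the somatostatin, insulin and glucagon infusions already running, which the plan should say.

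In Item 7, the eGFR entry and stopping limits must be reconciled, as must the status of dizziness relative to the hypotension rule. No clinical rule is proposed here.

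The cost is plan wording and a little programming, with no new data or participants. The downside is that the model assumes losses depend only on observed data, which is why the sensitivity analysis and the table are needed.
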